7.3 TREATMENT COMPLIANCE

Treatment compliance will be computed for both parts of the trial and for both routes of administration separately. Subjects receiving the full dose, and those that – due to any reason – did not, will be assessed. The outputs will show the number of subjects who have received the trial medication in accordance to the CTP as well as those who did not, including the initial dose level computed for the subjects. Only descriptive statistics are planned for this section of the report.

7.4 PRIMARY ENDPOINTS

- To evaluate the primary objective of evaluating the safety and tolerability of a single inhalation of DZIF-10c in SARS-CoV-2-uninfected and SARS-CoV-2-infected individuals, a toxicity-guided approach is utilised in this study.
- To evaluate the primary objective of evaluating the safety and tolerability of a single combined treatment with inhalation and intravenous infusion of DZIF-10c in SARS-CoV-2-uninfected and SARS-CoV-2-infected individuals, a toxicity-guided approach is utilised in this study.

All evaluations for the primary endpoints will be done on the subject set mTS in phase I and on the subject set TS in phase IIa.

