Statistical Methodology	
Quantitative data will be summarized by mean <math>\pm</math> standard deviation and percentiles (0, 25, 50, 75, 100), qualitative data by absolute and relative frequency. Listings of the data will be given where appropriate. Data up to the day 7 visit after study treatment and during follow up after the day 7 visit will be evaluated separately, and in total where sensible. Results are described by group (dose and SARS-CoV-2-infection group in the dose escalation phase, treatment group in the randomized phase) and in total.
 
Analysis cohorts include the safety population (as treated), including all trial participants who received any amount of the study drug, as well as the modified intention-to-treat (mITT) population in the expansion phase, including all randomized trial participants receiving study drug who have at least a baseline (day 0) value and a second measurement until (including) the day 7 visit after trial drug administration.
 
Statistical analyses are descriptive by nature. The frequency of (serious) adverse events ((S)AEs) and adverse events of special interest (AESIs) occurring up to the day 7 visit after study drug application, during study follow up after the day 7 visit and in total will be given. Safety events of the primary endpoints will be listed. Main analysis is in the safety population.
 
Secondary and exploratory endpoints will be summarized, figures may show development over time where appropriate. Additionally, explorative multivariable methods or confidence intervals may be calculated where sensible. Endpoints will be evaluated in the mITT population, and additional analysis populations can be defined. Viral RNA shedding determined by qRT-PCR will be evaluated as time weighted average change from baseline.
 
A full description of the statistical methodology will be provided in the Statistical Analysis Plan.

Funding	Funding for this trial is provided by Boehringer Ingelheim.

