### 5.7.1. Follow-Up after Withdrawal

In case of an early termination of a trial participant, the date and reason for early termination should be collected and reported to the Principal Investigator who will provide this information to the Sponsor and to the SMC. At the time of withdrawal and if the participant agrees, all procedures specified in the Final Study Visit according to the corresponding Visit Schedule (**Appendix II**) will be performed.

Any Adverse Event resulting in withdrawal of a participant will be followed up until resolution or until the adverse event is judged by the principal investigator or designee to have stabilized where possible.

Should a study participant become pregnant during the conduct of the clinical trial, separate informed consent for follow-up until delivery and for assessment of the newborn's health status or a report by the responsible pediatrician will be sought.

Participants who are withdrawn from the trial after DZIF-10c administration will not be replaced, except for participants during the dose-escalation phase of the trial that are not followed until at least the day 7 visit after inhalation for reasons not related to safety events.

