#### 8.1.1. Analysis Populations

##### Dose-Escalation Phase (Groups 1A-1C and Groups 2A-2C)

Analyses are conducted “as treated”, which includes all participants who received any amount of the study drug.

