##### Randomized Placebo-Controlled Phase (Group 2D)

The primary dataset for analysis is the safety population (as treated). This population includes all trial subjects who received any amount of the study drug.

The secondary dataset for analysis is a modified intention-to-treat (mITT) population. This dataset includes all randomized trial participants receiving study drug inhalation and infusion and who have at least a baseline (day 0) value and a second measurement of viral RNA shedding in nasopharyngeal swabs by qRT-PCR up to the day 7 visit. The evaluation is carried out strictly in accordance with the allocation by randomization.

Additional analysis populations can be defined in the SAP.

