#### **8.1.3. Primary Outcome and Target Variables**

Primary target variables are Adverse Events (including Serious Adverse Events and Adverse Events of Special Interest), as defined in chapter 5.2.1 and chapter 9. Evaluation will be performed in the safety population. Safety events will be listed by participant. Safety events are reported in total, by seriousness, relatedness, and severity.

Analysis is descriptive. Safety events will be evaluated as rate and frequency of participants who experienced the event and also as number of events.

Safety events will be evaluated in the time period until the day 7 visit after trial drug administration, after the day 7 visit until the end of study, and in aggregate. An exception are AESIs, which will be documented as AESIs until the day 7 visit only.

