6.3 SUBJECT SETS ANALYSED

- Screened set (SCS):
 - This subject set includes all subjects having signed informed consent and would correspond to the intention-to-treat set (ITT) in the phase I part of the trial.
- Randomised set (RS):
 - This subject set includes all randomised subjects in the phase IIa part of the trial, whether treated or not. This would correspond to the intention-to-treat set (ITT) in the phase IIa part of the trial
- Treated set (TS):
 - This subject set includes all subjects who received any amount of study drug.
- Modified Treated set (mTS):
 - This subject set includes all subjects who received any amount of study drug and did not require replacement in the phase I part of the trial. Details about requirement for replacement can be found below.
- Modified Intention-To-Treat set (mITT):
 - This subject set includes all randomised subjects in the phase IIa part of the trial that received any amount of study drug and who have at least a baseline value and a second measurement in the first week (up to 7 days after drug intake) of viral RNA shedding in nasopharyngeal swabs by qRT-PCR.

- PK parameter analysis set (PKS):
 - This subject set includes those subjects in the TS with at least one valid serum concentration of DZIF-10c available

Participants who are withdrawn from the trial after DZIF-10c administration will not be replaced, except for participants during the dose-escalation phase of the trial that are not followed until at least the day 7 visit after drug administration for reasons not related to safety events. Subjects who were replaced will be excluded from the primary analysis of the primary endpoint. Replacement of subjects will be determined on a case-by-case basis; exclusion of these subjects from the primary analysis will be confirmed by the trial team at the report planning meeting prior to database lock.

Please see [Table 6.3: 1](#) for a general overview which patient set will be used for which type of analyses. Additionally, biomarker analyses might be performed on subsets of the mITT set.

Table 6.3: 1 Subject sets used in the different types of analysis

Type of analysis	Subject set					
	SCS	RS	TS	mTS	mITT	PKS
Primary endpoints			X		X ^[1]	
Further endpoints				X		
Safety data, ADA & treatment exposure				X		
Demographic/baseline characteristics				X		
Disposition		X	X			
PK parameters						X
Viral Load				X ^{[1][2]}	X	

^[1] Will be used for the phase I part of the trial.

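### The SAP runs the phase I primary AE proportion on a set that drops replaced participants, whereas the protocol analyses everyone dosed, and the SAP does not list this as a change

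*SAP*

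**What the plan says.** **Protocol.** Section 8.1.1 analyses Groups 1A-1C and 2A-2C as treated, "which includes all participants who received any amount of the study drug". Section 8.1.3 says of the primary AE variables: "Evaluation will be performed in the safety population". The synopsis agrees: "Main analysis is in the safety population". Section 5.7.1 says that withdrawn participants are not replaced, "except for participants during the dose-escalation phase of the trial that are not followed until at least the day 7 visit after inhalation", and limits this exception to reasons unrelated to safety. It governs enrolment and removes nobody from an analysis.

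**SAP.** Section 6.3 defines the TS as all who received study drug, and the mTS as the TS without those who required replacement in phase I. It then states: "Subjects who were replaced will be excluded from the primary analysis of the primary endpoint". On process it says: "Replacement of subjects will be determined on a case-by-case basis". The trial team confirms the exclusions at a planning meeting before database lock. Section 7.4 makes the assignment: "All evaluations for the primary endpoints will be done on the subject set mTS in phase I and on the subject set TS in phase" (the second phase named being IIa).

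**Declaration.** SAP 4.2, which lists changes from the protocol, is silent on this. SAP 4.1 says only that Section 6.3 shows additional populations.

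**The concern.** The two documents name different phase I populations for the same primary endpoint, the proportion of participants with any AE within 7 days of dosing. Being followed to day 7 is a sensible condition for a 3+3 DLT denominator. It is not a reason to remove an exposed participant, or an AE already observed in that participant, from a first-in-human AE rate.

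The choice is also exposed to outcome knowledge. Phase I is open label (Protocol 5.9.6), its 7-day AE data are summarised at interim analysis 1 (SAP 9.1.1), and exclusions are settled case by case before lock. With three to six participants per group, one such decision moves the rate visibly.

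**Working it through.** **Step 1: planned size.** Protocol 4.1 gives six dose-escalation groups of 3 to 6. 6 × 3 = 18 and 6 × 6 = 36, which reproduces the 18(-36) in the synopsis. No document says how many participants, if any, were replaced.

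**Step 2: the sets side by side.**

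| | Phase I primary AE endpoint | Replaced but treated participants |
|---|---|---|
| Protocol 8.1.1, 8.1.3, synopsis | as-treated safety population | included |
| SAP 6.3, 7.4 | mTS | excluded |
| SAP 7.8 (other safety analyses) | TS by default | included |

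The protocol sentence that calls the safety population the primary dataset stands under the Group 2D heading, so it is not used here. For phase I the basis is the as-treated rule in 8.1.1, with 8.1.3 and the synopsis. The protocol sentence that allows further populations in the SAP also stands under Group 2D, and it allows additions rather than a substitute for the stated primary set.

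**Step 3: effect of one replaced participant (an assumption).** Let n be the number retained in a group, x the number of those with an AE, and y = 1 if the replaced participant had an AE before leaving, otherwise 0.

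- mTS rate = x/n
- TS rate = (x + y)/(n + 1)
- TS − mTS = (n − x)/[n(n + 1)] if y = 1, and −x/[n(n + 1)] if y = 0

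| n | x | y | mTS | TS | TS − mTS |
|---|---|---|---|---|---|
| 3 | 0 | 1 | 0/3 = 0% | 1/4 = 25% | 3/12 = +25 points |
| 3 | 1 | 1 | 1/3 = 33% | 2/4 = 50% | 2/12 = +17 points |
| 3 | 1 | 0 | 1/3 = 33% | 1/4 = 25% | −1/12 = −8 points |
| 6 | 0 | 1 | 0/6 = 0% | 1/7 = 14% | 6/42 = +14 points |
| 6 | 1 | 1 | 1/6 = 17% | 2/7 = 29% | 5/42 = +12 points |
| 6 | 1 | 0 | 1/6 = 17% | 1/7 = 14% | −1/42 = −2 points |

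Pooled over 18 retained participants, one replaced participant with an AE gives 0/18 = 0% against 1/19 = 5.3%, or 1/18 = 5.6% against 2/19 = 10.5%.

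**Step 4: is there a treated-set check within SAP 7.4?** Section 7.4.2 repeats the analyses over 28 days, over follow-up from day 9, and over the whole trial. These are evaluations of the primary endpoint, so the sentence in 7.4 puts them on the mTS too. They vary the time window but not the population.

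**The case against.** The strongest reply is that the mTS has a rationale and does little harm. Someone who leaves on day 2 without an AE has not completed the 7-day window, yet counts on the TS as a full non-event. Replacement is limited to non-safety reasons, so a participant who leaves because of an AE is not replaced and stays in the mTS. SAP 7.8 uses the TS by default and plans AE summaries for 7 days, 28 days and the whole trial, and events are listed by participant. The analysis is descriptive, and escalation follows the DLT rules and Safety Monitoring Committee review, not this proportion.

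All of that stands and limits the size of the point. It also rules out some stronger readings that a reader might infer:

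- **That the exclusion can only flatter the drug.** It can also raise the rate, as in 1/3 against 1/4.
- **That AEs would vanish from the report.** They remain in the treated-set tables and listings.
- **That the team may exclude whom it likes at the last moment.** The criterion is fixed in Protocol 5.7.1, and the SAP places confirmation before lock without saying how long before. What remains is discretion in applying the criterion.
- **That the mTS is concealed.** SAP 6.3 states the exclusion openly and 4.1 points there. Neither says that the primary set named in the protocol has changed.

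The reply does not remove the conflict. An AE on day 1 to 3 followed by an unrelated withdrawal still leaves the primary rate. The report could also show two 7-day AE proportions for one group, with the one labelled primary departing from the protocol.

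**Conclusion.** The point holds as a conflict over the phase I primary analysis set that SAP 4.2 does not declare. It affects the result labelled primary and its repeats in 7.4.2, not the completeness of safety reporting. Under the assumption of one replaced participant per group and no more than one AE among those retained, the mTS rate would lie 17 to 25 points below the TS rate with three retained, or 12 to 14 points below with six, if that participant had an AE. If that participant had none and one retained participant did, it would lie 8 or 2 points above. If nobody was replaced, the two sets coincide and no result changes. SAP 4.2 speaks of three subjects per cohort, which is compatible with no replacement but may only describe the planned size. The figures are therefore illustrations, and the documents do not support reading them as an actual distortion. It should be corrected because the correction is nearly free and removes an exclusion made with outcomes known from a first-in-human safety rate.

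**What to change.** 1. In SAP 7.4, name the TS for the phase I primary AE proportion and for its 7.4.2 repeats, as the protocol has it.
2. Keep the mTS only as the DLT-evaluable denominator, or as a labelled sensitivity analysis of the AE rate.
3. In SAP 6.3, delete the sentence "Subjects who were replaced will be excluded from the primary analysis of the primary endpoint", or restrict it to DLT evaluability.

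If the sponsor prefers the mTS as primary, the minimum is to list the change in SAP 4.2 with a reason and show both sets side by side.

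The cost is a wording edit and one population flag. The downside is that participants with incomplete 7-day follow-up count in the denominator; a footnote giving the number replaced in each group would make that visible. The escalation rules and decisions are untouched.

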7.4.1 Primary analysis of the primary endpoint

The primary endpoint analysis, implemented separately for phase I and phase IIa, will evaluate the proportion of patients with any adverse event occurring within 7 days of study drug administration.

As this study is exploratory and hypothesis generating in nature, no formal statistical testing will be implemented. Handling of missing data points is described in [Section 6.6.1](#). Please note that the number of events will also be provided in listings. All adverse events with onset during the first 7 days after drug administration will be taken into consideration for this endpoint analysis, and an overall summary of AE occurrences (N and %) will be created. In addition to the occurrence of adverse events the following AE attributes will be presented and evaluated:

- Severity / Maximum CTCAE grade
- Relatedness
- Outcome
- Time to first occurrence [days]

As one specific aim of the study is to determine a safe dose to be taken forward into subsequent development, the evaluation of dose-limiting toxicities (DLT) is of particular importance in the phase I part of the trial. A DLT for this trial will be defined as any grade 3 or higher adverse event that the investigators determine to be related to DZIF-10c. The following evaluations will therefore be implemented:

- Proportion of patients with DLTs after DZIF-10c inhalation occurring within 7 days of study drug administration.

Any AE meeting the criteria for DLT, regardless at which point in time after drug administration it occurred, will be considered a significant adverse event (SIAE). The analysis of non-serious SIAEs and serious adverse events (SAEs) is described in [Section 7.8.1](#) of this document.

7.4.2 Sensitivity analysis, subgroup analysis, exploratory analysis of the primary endpoint

The above analyses will be repeated on all adverse events, and adverse events meeting the criteria for DLT as shown in [Section 7.4.1](#) (irrespective of relatedness to treatment) and adverse events of special interest (AESIs) with onset from the date of administration of trial medication and up to 28 days after drug intake and during follow-up from day 9 to day 91. It will also be repeated on all adverse events, and all related adverse events meeting the criteria for DLT regardless of onset date for the whole trial duration leading to the following additional evaluations.

- Rate of Adverse Events after DZIF-10c administration occurring within 28 days of trial drug administration
- Rate of Adverse Events after DZIF-10c administration occurring at any time during trial participation

7.5 SECONDARY ENDPOINTS

As this study is exploratory and hypothesis generating in nature, no formal statistical testing will be implemented. Please note that any p-values will be considered nominal in nature and no adjustment for multiplicity will be made.

7.5.1 Key secondary endpoints

This section is not applicable as no key secondary endpoint has been specified in the protocol.

7.5.1.1 Primary analysis of the key secondary endpoints

This section is not applicable as no key secondary endpoint has been specified in the protocol.

7.5.1.2 Sensitivity analysis, subgroup analysis, exploratory analysis of the key secondary endpoints

This section is not applicable as no key secondary endpoint has been specified in the protocol.

7.5.2 Other Secondary endpoints

The same secondary endpoints have been defined for both parts of the trial. Due to the nature of the different trial parts, there may however be differences in the analysis of those endpoints.

7.5.2.1 Secondary endpoints phase I

7.5.2.1.1 AUC_{0-672h} (the area under the concentration-time curve of DZIF-10c in serum over the time interval from 0 to 672 hours (i.e. post drug administration until Day 29))

AUC_{0-672h} will be derived according to the relevant BI internal procedure. Descriptive statistics of PK parameters (a.o. Min, Median, Max) will be tabulated by cohort.

Please compare with [Section 7.6.1.9](#). This endpoint will be evaluated on the subject set PKS.

7.5.2.1.2 The frequency and magnitude of anti-drug antibodies targeting DZIF-10c

The ADA status (positive/negative) and ADA titer will be listed by cohort and overall. Descriptive statistics of ADA status (n, %) and ADA titer (Min, Median, Max) will be provided by cohort and overall, if data allows. Further exploratory characterization of ADA responses may be performed if data allows.

This endpoint will be evaluated on the subject set TS.

7.5.2.1.3 SARS-CoV-2 RNA shedding in nasopharyngeal swabs determined by qRT-PCR in SARS-CoV-2-infected individuals

Summary statistics of CT values as well as copies/ml based on a reference standard will be shown for each assessment time point by cohort and overall. This will be done for absolute values as well as relative and absolute change from baseline. All statistics will be calculated separately for the assessed SARS-CoV-2 genes (E gene and the ORF1a/b gene).

This endpoint will be evaluated on the subject set subject set TS who have at least a baseline value and a second measurement in the respective time period of viral RNA shedding in NP swabs by qRT-PCR.

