#### **5.2.4. Assessment of Anti-Drug Antibodies**

Serum samples will be analyzed for reactivity against DZIF-10c by a validated immunoassay.

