### Anti-Drug Antibodies

The frequency of participants with antibodies and magnitude (i.e., titer) of antibodies targeting DZIF-10c will be calculated and described in tables.

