5.2.2.2 The frequency and magnitude of anti-drug antibodies targeting DZIF-10c

The following parameters will be assessed:

- The number and percentage of subjects with anti-drug antibodies (ADA) on Day 1, 15, 29, 57 and 91 by cohort and overall
- For subjects with ADA: the ADA titer on Day 1, 15, 29, 57 and 91

5.2.2.3 SARS-CoV-2 RNA shedding in nasopharyngeal swabs determined by qRT-PCR in SARS-CoV-2-infected individuals

Viral shedding is quantified as viral load (VL) in nasopharyngeal swabs by using a SARS-CoV2-RNA qPCR assay, and reported as PCR threshold cycle (CT) values. The transformation of CT into units of copies/mL is performed by using assay reference standards.

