7.5.2.2.2 The frequency and magnitude of anti-drug antibodies targeting DZIF-10c

The same assessments will be performed as described in [Section 7.5.2.1.2](#).

This endpoint will be evaluated on the subject set TS.

7.5.2.2.3 SARS-CoV-2 RNA shedding in nasopharyngeal swabs determined by qRT-PCR in SARS-CoV-2-infected individuals

All evaluations for the first 7 days after drug administration will be done on the mITT set and will take data into consideration based on the time window around the corresponding visit as defined in [Section 6.7](#). The latest day to be taken into account is 7 days after drug administration. The evaluations for the later time points will be based on all subjects in the subject set TS who have at least a baseline value and a second measurement in the respective time period of viral RNA shedding in NP swabs by qRT-PCR.

Absolute viral load in SARS-CoV-2-infected individuals, as well as absolute and relative changes from baseline, will be summarised descriptively for each assessment time point and plotted by treatment arm and listed.

Time-weighted average change in viral load

The evaluation of viral load will be done by a time-weighted average change in \log_{10} viral load from baseline, defined by:

$$\frac{\sum_{i=a}^{b-1} \{0.5 * (Y_i + Y_{i+1}) * (t_{i+1} - t_i)\}}{(t_b - t_a)}$$

where

- Y_i = change from baseline in \log_{10} viral load at visit i
- t = time at the specified time point (the actual study day)
- a = baseline assessment at day 1
- b = last assessment at or prior to the threshold day (7 days after drug intake)

A parametric analysis of covariance (ANCOVA) model with corresponding baseline viral load and antibody status will be used. Adjusted means and 95% confidence intervals (CIs) will be provided. Missing values will not be imputed and since a linear trajectory on the log scale is expected, the normalisation by the denominator assures comparability of the values if t_b is different between patients.

Ratios between means (DZIF-10c vs placebo) will be calculated for each treatment arm separately for the respective time period. These calculations will be based on the mean time-weighted average change in viral load based on the ANCOVA model. CIs for the ratios will be reported for which the Delta method (Taylor method) will be used to calculate the variance of the ratios.

Mixed effect Model for Repeated Measures (MMRM)

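### Phase IIa anti-drug antibody negatives are not read against the DZIF-10c level in the same sample, so ADA frequency in the inhaled-plus-infusion arm could be understated

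*SAP*

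**What the plan says.** Protocol 5.2.4 describes the assay in one sentence: "Serum samples will be analyzed for reactivity against DZIF-10c by a validated immunoassay". No sensitivity, cut-point or drug-tolerance limit follows. Protocol 8.1.4 makes titer part of the endpoint: "The frequency of participants with antibodies and magnitude (i.e., titer) of antibodies targeting DZIF-10c will be calculated and described in tables".

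SAP 5.2.2.2 sets the time points: "The number and percentage of subjects with anti-drug antibodies (ADA) on Day 1, 15, 29, 57 and 91 by cohort and overall". In the SAP's day numbering these are baseline and 14, 28, 56 and 90 days after dosing. All times below are days after dosing.

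SAP 7.5.2.1.2 (phase I) gives the analysis: "The ADA status (positive/negative) and ADA titer will be listed by cohort and overall". It adds "Descriptive statistics of ADA status (n, %) and ADA titer (Min, Median, Max) will be provided by cohort and overall, if data allows" and "Further exploratory characterization of ADA responses may be performed if data allows". For phase IIa, SAP 7.5.2.2.2 only refers back: "The same assessments will be performed as described in" the phase I section. SAP 7.5.2.2 puts the phase IIa summaries by treatment arm.

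Unless a section says otherwise, SAP 7 takes percentages over all subjects in the analysis set, including those with missing values. The ADA sections do not say otherwise. The visit schedule for infected participants (Protocol Appendix II B) has PK samples at every ADA visit.

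**The concern.** Drug in a serum sample can compete with the assay reagent for anti-drug antibody. A negative result is then informative only when the drug concentration is within the assay's tolerance. The plan has two status categories, so a sample that the assay could not read would be tabulated as negative and kept in the denominator.

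This would not fall evenly on the arms. One active arm receives inhaled drug only. The other receives the same inhaled dose plus a large infusion, which Protocol 5.9.5 justifies partly by lasting systemic activity. Any masking would therefore sit mainly in the infusion arm and make the combined regimen look less immunogenic than inhalation alone.

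The SAP does set assay-limit rules elsewhere. Viral load has a rule for values below the quantification limit (SAP 5) and a non-missing denominator for clearance (SAP 7.5.2.2.3). ADA has no counterpart. The second interim analysis (SAP 9.1.2.3) also includes preliminary ADA results if data allow, and the post-dose samples available then would lean towards early visits, when drug levels are highest.

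**Working it through.** The documents give no ADA rate, drug tolerance, DZIF-10c concentration or half-life, so there is no figure of the plan's own to reproduce. The steps below ask how large the imbalance between arms is, and at which visits it could matter.

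**Step 1: dose ratio.** The inputs from the documents are 250 mg inhaled and a target of 40 mg/kg intravenous. Body weight w is assumed.

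- Infusion / inhaled dose = 40w / 250. At 50, 70 and 100 kg this is 2,000/250 = 8, 2,800/250 = 11.2 and 4,000/250 = 16.
- Total systemic dose, combined arm over inhaled-only arm, with inhaled bioavailability F (assumed): (40w + 250F) / (250F). At 70 kg: F = 100% gives 3,050/250 = 12.2; F = 10% gives 2,825/25 = 113; F = 1% gives 2,802.5/2.5 = 1,121.

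**Step 2: serum level from the infusion.** One-compartment decay, C(t) = (dose/V) × 0.5^(t / half-life). Assumed: 70 kg (2,800 mg), V = 3 or 6 L, half-life = 7, 14, 21 or 28 days, which makes 8 combinations. The lowest value is always V = 6 L with 7 days, and the highest is V = 3 L with 28 days. For example, at day 14 the lowest is 2,800/6 × 0.25 = 116.7 and the highest is 2,800/3 × 0.707 = 660.0 µg/ml. The last column counts combinations above four assumed tolerances.

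| Days after dosing | Lowest, µg/ml | Highest, µg/ml | Combinations of 8 above 10 / 50 / 100 / 500 µg/ml |
|---|---|---|---|
| 14 | 116.7 | 660.0 | 8 / 8 / 8 / 2 |
| 28 | 29.2 | 466.7 | 8 / 7 / 6 / 0 |
| 56 | 1.8 | 233.3 | 6 / 5 / 3 / 0 |
| 90 | 0.1 | 100.6 | 5 / 2 / 1 / 0 |

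With inhalation only at an assumed 5% bioavailability (12.5 mg), the day-14 level is about 0.5 to 3 µg/ml, below all four tolerances.

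**Step 3: effect on a table with 20 per arm.** Let the true ADA rate be p and the detected fraction s, both assumed. Then P(no positive among 20) = (1 − ps)^20.

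- p = 10%: 0.90^20 = 12% with full detection, 0.95^20 = 36% with half detected, 0.975^20 = 60% with a quarter detected.
- p = 20%: 0.80^20 = 1%, 0.90^20 = 12% and 0.95^20 = 36%.

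With the same true rate in both arms, partial masking in one arm can readily produce a zero there.

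**The case against.** The strongest reply is that interference is unproven. The assay is described as validated, and its drug tolerance may be adequate and recorded outside these documents. At 500 µg/ml, no value in the grid from day 28 onward would be unreadable. That stands, and the point has to be conditional. A reader might infer that the infusion arm's ADA rate is biased downward as a matter of fact; the documents do not support that.

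A reader might also infer that ADA is reported only as positive or negative. It is not: titer is listed and summarised, and further characterisation is allowed. This does not close the gap, because a masked sample has no titer and drug can also depress the titer of a positive one.

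A reader might further infer that the arms differ in exposure by orders of magnitude at every visit to day 90. The doses alone support 8 to 16 times. Larger ratios need an assumed low bioavailability, and half-life is something that the trial itself will estimate. The target infusion dose may be reduced, and the Safety Monitoring Committee decides whether the infusion is included at all (Protocol 3.4).

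Three more replies carry some weight. Serum concentrations and ADA results are both listed, so a careful reader could match them; what is missing is the rule and its effect on the summary table. No formal ADA comparison between arms is planned, yet a table of percentages by arm invites one. Finally, the analysis text sits in the phase I section, where every group is inhalation-only; the problem arises only when phase IIa adopts it.

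**Conclusion.** The gap is real and specific to phase IIa. Two-category status, a default denominator of all subjects and no link to concurrent drug level mean that uninformative negatives can be counted as true negatives, mainly in the inhaled-plus-infusion arm. The infusion is 8 to 16 times the inhaled dose at an assumed 50 to 100 kg and the 40 mg/kg target, and the systemic imbalance is larger if inhaled bioavailability is low.

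Whether negatives are in fact masked depends on an unstated drug tolerance. Under the assumed weight, volume and half-lives, masking is most plausible at days 14 and 28. It is uncertain at day 56, where only 3 of 8 combinations exceed 100 µg/ml, and not established at day 90. Severity is minor to moderate: the endpoint is secondary, descriptive and untested, but its by-arm percentages could mislead later development.

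**What to change.** In SAP 5.2.2.2, 7.5.2.1.2 and 7.5.2.2.2:

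- State the assay's validated drug tolerance.
- Merge each post-dose ADA result with the DZIF-10c concentration from the same visit.
- Class each sample as positive, negative (no ADA detected, drug at or below tolerance) or inconclusive (no ADA detected, drug above tolerance).
- Report all three counts by arm and visit, over all subjects with an ADA sample at that visit.
- Do not compute a rate as positive / (positive + negative). That keeps positives at any drug level and drops negatives above tolerance: 2 positive and 18 inconclusive would read as 2/2 = 100%.
- Where inconclusive samples exist, label positives over all sampled (here 2/20 = 10%) as a lower bound.
- Base any statement comparing the active arms on visits where samples in both are readable. Apply the same rule to the preliminary ADA output at the second interim analysis.

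The cost is SAP wording and a merge of data already scheduled; no sample, visit or sample size changes. The downside is fewer interpretable samples in the infusion arm. If the tolerance is adequate, the inconclusive count is zero and nothing is lost.
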